## 9.4 Reporting Procedures

All adverse events occurring after KB103 administration observed by the investigator or reported by the subject (whether or not attributed to investigational product), are reported on the case report form.

Medically significant adverse events considered related to the investigational product by the investigator or the sponsor are followed until resolved or considered stable. The investigator must assign the following attributes: description; dates of onset and resolution; severity; assessment of relatedness to investigational product, and action taken. The investigator may be asked to provide follow-up information.

All deaths occurring on study must be reported to Krystal. These include deaths during the Long-Term Follow-Up period. For all deaths, available autopsy reports and relevant medical reports may be requested.

The investigator should notify the IRB of serious adverse events occurring at the site and other adverse event reports received from the sponsor, in accordance with local procedures.

It is left to the investigator’s clinical judgment whether or not an adverse event is of sufficient severity to require the subject’s removal from study. A subject may also voluntarily withdraw from study due to what he or she perceives as an intolerable adverse event. If either of these occurs, the subject is asked to undergo an early termination assessment and be given appropriate care under medical supervision until symptoms cease or the condition becomes stable. If the subject was permanently withdrawn from the study due to a serious adverse event, this information must be included in either the initial or follow-up Serious Adverse Event Report Form, and in the End of Study Case Report Form.

**9.4.1 Post-KB103 Administration Adverse Event Monitoring**

The Investigator must monitor the subject's treated and paired, non-treated wounds closely for additional blister formation and expansion of the border.

**9.4.2 SAE Reporting Procedures**

All Serious Adverse Events (SAEs) that occur after the time of informed consent must be reported to Krystal and the IRB. All subjects with an SAE must be followed and the outcomes reported. The Investigator should supply the Sponsor and the IRB with any additional requested information (e.g., hospital discharge summary, autopsy reports and terminal medical reports). The Sponsor shall evaluate all SAEs and determine if they meet FDA reporting requirements. In the event of an SAE, the Investigator must:

1. Notify Krystal within 24 hours of the Investigator's awareness of the event.
2. Obtain and maintain all pertinent medical records, information, and medical judgments from colleagues who assisted in the treatment and follow-up of the subject.
3. Provide Krystal with a complete, written case history, including copies of supporting reports (e.g., progress notes, laboratory reports) and a statement from the Investigator as to whether or not the event was related to the use of the investigational product.
4. Promptly inform the governing IRB of the event, if it is related. For other SAEs, notify the governing IRB as required by the IRB, local regulations, and the governing health authorities.

## 10 Statistical Considerations

Post-screening procedures occur as outlined in the Schedule of Events. The end-of-treatment (or treatment endpoint) is also defined as the last assessment time point for efficacy evaluations in order to handle the issue of missing data that is caused by incomplete data collection or early terminations.

### 10.1 Number of Subjects

A formal sample size calculation was not performed for this study. The sample size is based on what was considered an adequate number of subjects for a pilot study to obtain sufficient information on the safety and effectiveness of KB103.

### 10.2 Data Management

An electronic case report form (eCRF) is used to collect information for safety and proof of mechanism analyses. A clinical database is managed by a sponsor's representative for this study. The database is constructed based on the CRF data entry plus laboratory data information. Data queries are generated and resolved. In addition, range checks of the CRF fields, plausibility and consistency checks across CRF pages will be performed to assess consistency, accuracy and completeness of the data collected and entered into the CRF. Standard SAS datasets are generated and provided for analysis.

### 10.3 Study Populations

The primary population for an analysis of the proof of mechanism is the intent-to-treat (ITT) population. Study populations are defined in the following sections.

#### 10.3.1 Safety Population

This population is defined as all subjects who were administered KB103.

#### 10.3.2 Intent-to-Treat Population

The intent-to-treat (ITT) population includes subjects who were administered KB103 who have had at least one paired assessment of the target wound area post-administration, i.e., at least one KB103 target wound and one placebo target wound.

#### 10.3.3 Per-Protocol Population

The per-protocol (PP) population is defined as all subjects in the ITT population who have had at least one paired assessment of the target wound area post-administration, and completed the protocol as planned.

## 10.4 Demographic and Baseline Characteristics

The descriptive summaries of subjects' demographic and baseline characteristics are presented by treatment group for the safety, ITT, and PP populations. A detailed description of subject disposition is provided.

Subject characteristics include a summary of the following:

- Subject demographics.
- Baseline disease characteristics as determined at screening.
- Pre-existing medical conditions.

Continuous variables are summarized using number of observations, mean and standard deviation, median, and minimum and maximum values. Categorical values are summarized using number of observations and percentages.

## 10.5 Proof of Mechanism Analyses

### 10.5.1 Expression of Collagen VII

Biopsies collected for the purpose of IF are evaluated for expression of collagen VII by a qualified reader.

### 10.5.2 Production of Anchoring Fibrils

Biopsies collected for the purpose of IEM are evaluated for the presence of anchoring fibrils by a qualified reader.

### 10.5.3 Target Wound Area

Target wound surface area is obtained through on-site and at-home imaging of target areas. Change in area from baseline is evaluated for using a paired t-test for each KB103 target wound vs. control wound.

Time to closure and durability of closure will be assessed after each cycle of administrations.

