## 2 Objectives

### 2.1 Primary

- 1) To assess wound closure through post-administration imaging:
  - a. Change in surface area of a KB103-administered wound relative to the same wound at baseline and the placebo administered wound
  - b. Time to wound closure of a KB103-administered wound relative to a placebo-administered wound
  - c. Duration of wound closure of a KB103-administered wound relative to a placebo-administered wound

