### **6.3      Wound Area Selection**

Up to three wound areas are selected to be part of the study: one or two to receive KB103, and one to receive placebo. Final selection of the wound areas occurs at baseline. The following is considered when selecting target wound areas:

- **Wound areas can consist of one wound, or multiple wounds, and can include intact skin.**
- **The size of the wound area.** Target wound areas have a surface area up to 50 cm^2.
- **The location of the wound area.** Appropriate sites are on the anterior and/or lateral trunk and/or upper and/or lower extremities in areas protected from frequent trauma or injury. Excluded areas include the face, and areas close to mucous membranes (genitourinary, oral or anal mucosa).

- **The appearance of the wound.** Wounds should appear clean with adequate granulation tissue, excellent vascularization, and not appear infected.
- **Historical consistency in size of the wound.** A wound with a historically more consistent surface area is chosen over a less consistently sized wound.
- **The similarity of the wounds.** To the extent possible, similarity in location on the body should be considered.
- Wounds that have previously been administered investigational gene or cell therapy (except for previous KB103 administration) are not eligible for KB103 and placebo administration.

The Investigator will first selection two areas; one for KB103 and one for placebo. If another area meets the criteria above, it will be considered for inclusion in the study to receive KB103.

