6.1 General Conventions

The following general comments apply to all statistical analyses and data presentations:

- Summaries will include frequency and percentages for categorical data; frequency and median for ordinal data; and frequency, mean, standard deviation, and median, minimum, and maximum for quantitative data.
- Duration variables will be calculated using the general formula (end date – start date) +1.
- Change from baseline will be calculated for each subject at the specified time point as the value at the specified time point minus the baseline value.
- Individual subject listings of all data represented on the eCRFs will be provided to facilitate the investigation of tabulated values and to allow for the clinical review of all efficacy and safety parameters.
- Version 9.1.3 (or higher) of SAS® statistical software package will be used to provide all summaries, listings, graphs, and statistical analyses.

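### Primary objective 1a is tested in protocol 10.5.3 on unscaled wound area although starting sizes are not matched, and the SAP analyses the objective differently: state one paired, baseline-scaled comparison in both

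*Protocol*

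**What the plan says.** Protocol 2.1 lists as primary objective 1a "Change in surface area of a KB103-administered wound relative to the same wound at baseline and the placebo administered wound". The only test given for it is in protocol 10.5.3: "Change in area from baseline is evaluated for using a paired t-test for each KB103 target wound vs. control wound". No scale is named there. SAP 6.1 defines change from baseline generally as "calculated for each subject at the specified time point as the value at the specified time point minus the baseline value", which is an absolute difference.

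On starting size, protocol 6.3 says "Target wound areas have a surface area up to 50 cm"² and sets no minimum. An area may hold one or several wounds and may include intact skin. For likeness within a pair, it says only "To the extent possible, similarity in location on the body should be considered". The entry on historical consistency in size concerns the stability of one wound over time, not a match between two. On assignment, 6.3 says "The Investigator will first selection two areas; one for KB103 and one for placebo". Version 4.0 describes no randomisation step, whereas SAP sections 3 and 8 describe the studies as randomised.

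Protocol 1.6 reports, from imaging of the version 2 patients, that the form and size of a wound strongly influence how it heals under KB103.

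The SAP covers all data from Phase I through Phase II. Its Phase II objective (a), in 2.2.1, is the proportion of wounds with complete closure at weeks 8, 10 and 12. Section 8.1.1 tests this with a Cochran-Mantel-Haenszel (CMH) test on a reduction of at least 90% from the wound's own baseline. The only continuous area comparison is percent reduction, by Wilcoxon rank-sum test, among the other analyses that follow 8.1.1.1. The SAP contains no paired t-test on change in area.

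**The concern.** A wound cannot lose more area than it starts with, so a change in cm² carries the starting size with it. Two wounds that heal by the same fraction show different changes if they start at different sizes, and the paired difference then reflects size as well as treatment. Pairing within a subject removes what the two wounds share, but not a difference in size between them.

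Two consequences need to be kept apart. If it is chance which wound of a pair is larger, size differences inflate the variance of the paired difference and cost power. If KB103 wounds tend to be larger, the test leans towards KB103; if they tend to be smaller, it leans against. Investigator selection with no size rule and no described randomisation leaves the second possibility open in version 4.0.

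The conflict between the documents adds to this. A reader of the protocol expects a paired test on continuous area for a primary objective. A reader of the SAP finds a closure proportion in its place, and a continuous comparison that ignores the pairing.

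**Working it through.** **No figure to reproduce.** Neither document gives a power, effect size, standard deviation or wound-size distribution, and protocol 10.1 says that no formal sample size calculation was done.

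**Algebra.** Let A be baseline area and h the fraction healed, with K for KB103 and P for placebo.

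- Raw change of a wound: (1 − h)A − A = −hA.
- Paired difference on raw change: −(h_K·A_K − h_P·A_P). With equal healing h, this is −h(A_K − A_P).
- Paired difference in percent of baseline remaining: −100(h_K − h_P). Size drops out.

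Example: a 40 cm² KB103 wound and a 20 cm² placebo wound both halve. The raw changes are −20 and −10, a difference of 10 cm² in favour of KB103 with no drug effect. Swap the sizes and it is 10 cm² against. If both orders are equally likely, these average to zero and only variance remains.

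**Inputs from the documents.**

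- Size limits by protocol version (SAP section 3): up to 10 cm² for 2 patients (v1.0), up to 20 cm² for 4 + 5 = 9 patients (v2.2 and v3.x), and up to 50 cm² for 3 planned patients (v4.0). The total is 2 + 9 + 3 = 14, which agrees with the protocol synopsis. SAP 4.1 gives up to 12.
- Test level: one-sided 5% (SAP section 8).

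**Assumed inputs, not in the documents.**

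- Baseline area is lognormal with median 10 cm² and SD of log area 0.8, held at the version's limit. Within-pair log correlation is 0 or 0.5.
- Healed fraction is beta-distributed with SD 30 points and independent of size. The mean is 65% vs 35% for power, and 50% vs 50% for the false-positive rate.
- There is one pair per subject.

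**Results by simulation, 14 pairs, version-specific limits** (ranges run over the two correlations):

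| Quantity | Raw change | Percent change |
|---|---|---|
| Power | 50–56% | 78% |
| False positives, no systematic size difference | 5% or less | 5% |
| False positives, KB103 median 1.5 times larger | 17–19% | 5% |
| False positives, KB103 median 2 times larger | 30–33% | 5% |

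The power ratio is 50/78 = 0.64 to 56/78 = 0.72. The size multiple applies before the limits, which pull the realised ratio of sizes below 1.5 or 2.

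**Sensitivity to the assumptions.**

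- A 50 cm² limit for all 14 pairs: power 41–49% raw vs 78%, and false positives 21–24% and 41–48% at 1.5 and 2 times. This limit does not apply to 11 of the 14 patients.
- 12 pairs, version-specific limits: false positives 15–17% and 25–28%.
- 3 pairs (this version's enrolment): false positives about 6% and 8%, and power only 10–23% across both scales.
- A different model (sizes uniform on 5–50 cm² and independent, 70% vs 40% healed, SD 25 points, 14 pairs, one-sided): 61.8% vs 89.9%, ratio 61.8/89.9 = 0.69.
- Over a wider grid of sizes, effects and n (3, 12, 14), the ratio ran from 0.12 (n = 3, very wide size spread) to 1.00 (equal sizes).

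**Limit of the percent scale.** Its 5% rate above follows from assuming that healed fraction does not depend on size. Suppose instead that larger wounds heal a smaller fraction (assumed 15 points per log unit), with 14 pairs, KB103 wounds 1.5 times larger and no drug effect. The percent test then falsely favours placebo about 15% of the time. This is why a baseline-size covariate is needed as well.

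**The case against.** The strongest answer is that the SAP sets out the full analysis and does not run the raw-area test. Its lead analysis and its continuous comparison are both scaled to each wound's own baseline. That stands, and it narrows the point: the raw test exists in the protocol only. It does not remove the point. Protocol 10.5.3 is unchanged, objective 1a remains primary there, and the SAP's percent comparison is unpaired and has no size term.

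Second, 10.5.3 does not say cm². That is also fair. The unit is an inference from the wording and from the SAP's general convention, so the text could be called under-specified. Either way it needs to name a scale.

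Third, a reader might infer that any size difference is counted as a drug effect. The documents do not support this. No document says that KB103 wounds were larger, and the SAP calls the studies randomised. If size order is random, the false-positive rate is not raised.

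Fourth, a reader might infer that power is roughly halved. That follows only from particular assumptions, such as a 50 cm² limit for every patient. With the limits that the SAP lists, the loss is smaller under the same model, and it vanishes when sizes are equal. In version 4.0 the 50 cm² also bounds an area that may include intact skin, not a wound.

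Finally, this is a pilot with no stated power, so a loss of power breaks no promise in the plan.

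**Conclusion.** The point holds as an analysis choice worth correcting and as a conflict between the documents. Protocol 10.5.3 tests a primary objective on unscaled change, with no size matching and with size named as important to healing. The SAP replaces that analysis and does not restore a paired continuous one.

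The established cost is added noise. Bias is possible but conditional on a systematic size difference that the documents neither show nor exclude. The power and false-positive figures illustrate the mechanism under assumed sizes and healing fractions and are not estimates for this trial; with 3 pairs, power is low on either scale. For a pilot without a power claim this is a recommended correction, and it does not invalidate the plan.

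**What to change.** Reconcile protocol 10.5.3 with SAP 8.1.1 by stating the same continuous analysis of objective 1a in both: the paired within-subject difference, KB103 minus placebo, in percent of baseline area remaining. This replaces the t-test on raw change and the unpaired rank-sum comparison. Because SAP section 3 lists two KB103 wounds and one placebo wound for most patients, say how two KB103 wounds in one subject enter the paired difference.

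Add a sensitivity model that regresses this difference on the within-pair difference in log baseline area, since percent change is itself distorted if healed fraction depends on size. Keep raw cm² as a listing. State in both documents how areas are assigned to KB103 or placebo in version 4.0, so that a reader can judge whether a systematic size difference is possible.

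The cost is wording. Baseline area is already measured by imaging. The covariate uses one degree of freedom: in the simulation with 14 pairs and size irrelevant to healing, power was 75–76% with it and 78–79% without. The SAP's introduction says that a partial analysis came before it, so the date and reason for the change should be recorded.

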## Protocol Synopsis

Title	A Phase II Study of KB103, a Non-Integrating, Replication-Incompetent HSV Vector Expressing the Human Collagen VII Protein, for the Treatment of Dystrophic Epidermolysis Bullosa (DEB)
Objectives	
Primary
 
 
1) To assess wound closure through post-administration imaging:           
 
a. Change in surface area of a KB103-administered wound relative to the same wound at baseline and a placebo-administered wound
 
b. Time to wound closure of a KB103-administered wound relative to a placebo-administered wound
 
c. Duration of wound closure of a KB103-administered wound relative to a placebo-administered wound
 
 
 
 
Secondary
 
 
1) To assess change from baseline in the Investigator's Global Assessment score
 
2) To assess change from baseline in PRO scales of severity and pain
 
 
Other
 
 
1) To evaluate the expression of human collagen VII as determined by immunofluorescence (IF).
 
2) To evaluate the presence of anchoring fibrils as determined by immunoelectron microscopy (IEM) post-administration.
 

Test Product	KB103
# of Subjects	Up to 14 including Phase 1 and Phase 2. This version of the protocol intends to enroll 3 subjects.

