### 10.5.4 Investigator's Global Assessment

Investigator's Global Assessment (IGA) score on the target wound is obtained at baseline and post-baseline visits as outlined in the schedule of events. IGA scores will be evaluated at baseline and for post-baseline visits, using a paired t-test for each KB103 target wound vs. control wound.

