2.2.2 Other

- 1) To evaluate the expression of human collagen VII as determined by immunofluorescence (IF)
- 2) To evaluate the presence of anchoring fibrils as determined by immunoelectron microscopy (IEM) post-administration

3 Overview

The Phase I/II studies were randomized placebo controlled intrasubject comparison of KB103-administered and placebo-administered wounds.

To date, KB103 has been administered to 12 patients enrolled onto 4 versions of the Phase I/II protocol. A summary of the protocols and patients enrolled are presented below.

Phase	Protocol:	SN and Date:	# of pts	Wound size	# of wounds treated	Dose	Dosing days
1	v1.0, 19Apr2018	SN0001, 4/20/2018	2, Pts 01-02 Adults	Up to 10cm ²	2: one KB103, one placebo	1e8 PFU/wound/day	0, 2, 14, 28, 30
Following v1.0, the protocol was amended to increase the frequency and PFU level of the doses, and to administer to patients age 5 and older.							
2a	v2.2, 08Oct2018	SN0008, 10/09/2018	4, Pts 03-06 2 adults, 2 children age 13&14	Up to 20 cm ²	3: two KB103, one placebo	3e8 PFU/wound/day with the option to escalate to 6e8 PFU/wound/day	1, 2, 3, 4, 5, 30, 60, 90
Following 2.2, the protocol was amended to administer KB103 every two to three days to correspond with bandage changes. The potential number of doses increased, and the dose level was set at 2e8 PFU/wound/administration.							
2b	v3.1, 12Mar2019 and v3.2*, 25Jun2019	SN0016, 3/4/2019	5, Pts 07-11 3 adults, 2 children age 14&15	Up to 20 cm ²	3: two KB103, one placebo	2e8 PFU/wound/day	Every 2 to 3 days up to 15 per month
Following 3.2, the protocol was amended to administer KB103 in 2 cycles. The age of inclusion was reduced to 2 years old. Wound areas increase to up to 50cm ² , and with the increase in area the dose was increased to 6e8 PFU per area.							
2c	v4.0, 01Aug2019	SN0024, 8/5/2019	3, TBD	Up to 50 cm ²	Up to 3; 2 KB103 and one placebo	6e8 PFU/wound/day	Every 2 to 3 days until wound closure x 2 cycles

*v3.2 clarified the long-term follow-up

4 Study Implementation

Detailed information for the protocol study visits, is provided in the sections below and in the Schedule of Events ([Appendix 1: Schedule of Events](#)).

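### No rule says how two KB103 wounds are set against one placebo wound; pooling the pairs would raise a one-sided 5% error to about 8.5–9.5% when most or all subjects have two

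*Protocol*

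**What the plan says.** For wound area, protocol section 10.5.3 reads: "Change in area from baseline is evaluated for using a paired t-test for each KB103 target wound vs. control wound". Section 10.5.4 analyses IGA "using a paired t-test for each KB103 target wound vs. control wound", and section 10.5.5 uses the same wording for the PRO pain ratings.

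On wounds per subject, protocol section 6.3 says: "Up to three wound areas are selected to be part of the study: one or two to receive KB103, and one to receive placebo". The second KB103 area is optional: "If another area meets the criteria above, it will be considered for inclusion in the study to receive KB103". The table in SAP section 3 (Overview) gives "2: one KB103, one placebo" for the two version 1.0 subjects and "3: two KB103, one placebo" for the four version 2.2 and five version 3.1 subjects. For the current version the synopsis says "This version of the protocol intends to enroll 3 subjects", and for the whole study "Up to 14 including Phase 1 and Phase 2".

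Protocol section 10 gives no significance level, no sidedness, no rule for combining two KB103 wounds and no multiplicity rule. The ITT definition asks for at least one KB103 and one placebo wound, which does not settle the matter. SAP section 8 sets 5% one-sided. For wound area it uses Cochran-Mantel-Haenszel and Wilcoxon rank-sum tests in place of the paired t-test. It contains no analysis of IGA or PRO, which are the protocol's two secondary objectives.

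**The concern.** The wording can be read in two ways. The pairs may be pooled, so that a subject with two KB103 wounds contributes two differences, both taken against the same placebo wound. A paired t-test treats those differences as independent, which they are not, so the standard error is too small. Alternatively, one test may be run per KB103 wound. Each subject then enters a given test once, but there are two tests and no rule for reading them together.

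At stake is the error rate of whatever is reported from these sections. That matters most for IGA and PRO, where the protocol test is the only one stated in either document.

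**Working it through.** The documents give no error rate for this test, so there is no figure to reproduce.

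**Inputs.** Wounds per subject come from protocol section 6.3 and SAP section 3; the level of 5% one-sided comes from SAP section 8. Neither document gives a standard deviation or a correlation. I assume normal changes, equal variance σ² for all wounds and a common within-subject correlation ρ. Two-sided results are shown for comparison.

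**Step 1: correlation from the shared control.** Let d1 = K1 − P and d2 = K2 − P.
- Var(d) = 2σ²(1 − ρ)
- Cov(d1, d2) = ρσ² − ρσ² − ρσ² + σ² = σ²(1 − ρ)
- Correlation = 0.5, whatever ρ is.

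**Step 2: pooled pairs, every subject with two KB103 wounds, large sample.** The variance of the mean of 2n differences is Var(d)(1 + 0.5)/(2n), which is 1.5 times what the t-test assumes.
- One-sided: 1 − Φ(1.645/√1.5) = 1 − Φ(1.343) = 9.0%
- Two-sided: 2[1 − Φ(1.960/√1.5)] = 2[1 − Φ(1.600)] = 11.0%

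**Step 3: separate tests, large sample.** Each test has 5% error. With correlation 0.5, the bivariate normal probability that at least one rejects is 8.8% one-sided and 9.1% two-sided. Two independent tests would give 1 − 0.95² = 9.75%. Sharing the control therefore lowers this figure slightly; the excess over 5% comes from having two tests.

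**Step 4: actual sample sizes.** These are simulated t-tests with 200,000 to 400,000 replicates. Of the 12 treated subjects in the SAP, 2 + 4 + 5 = 11 belong to earlier versions and one to version 4.0, so 9 or 10 of the 12 have two KB103 wounds.

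| Subjects with two KB103 wounds | Pooled, 1-sided | Pooled, 2-sided | At least one of two tests, 1-sided | At least one of two tests, 2-sided |
|---|---|---|---|---|
| v4.0: 3 of 3 | 9.6% | 11.3% | 9.3% | 9.5% |
| v4.0: 2 of 3 | 8.6% | 9.7% | 9.4% | 9.7% |
| v4.0: 1 of 3 | 7.0% | 7.5% | 5% (second test impossible) | 5% |
| v4.0: 0 of 3 | 5% | 5% | 5% | 5% |
| v2.2 and v3.1: 9 of 9 | 9.1% | 11.2% | 8.9% | 9.2% |
| All treated: 9 of 12 | 8.6% | 10.3% | 9.1% | 9.4% |
| All treated: 10 of 12 | 8.8% | 10.6% | 9.0% | 9.3% |
| Full enrolment: 12 of 14 | 8.8% | 10.6% | 8.9% | 9.2% |
| Full enrolment: 9 of 14 | 8.3% | 9.8% | 9.1% | 9.4% |

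**Step 5: one averaged difference per subject.** Var[(K1 + K2)/2 − P] = 1.5σ²(1 − ρ), against 2.0σ²(1 − ρ) for a single KB103 wound: 25% smaller. Simulated error is 4.9–5.1% in these configurations.

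**Step 6: unequal variances (assumed range).** With placebo-to-KB103 variance ratios from 0.25 to 4, three subjects and two KB103 wounds each, pooled error runs from 6.6% to 13.2% one-sided and from 7.1% to 17.7% two-sided. At least one of two separate tests rejects in 8.4–9.6% one-sided and 8.9–9.8% two-sided.

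**The case against.** A reader might infer that the false-positive rate is 9–11% under either reading and that the placebo wound is always used twice. The documents do not support that, for four reasons.

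- **The second KB103 area is conditional.** Version 4.0 allows one, and version 1.0 had only one. A scenario in which all 12 treated subjects have two KB103 wounds contradicts the SAP's own table.
- **Eleven per cent needs a two-sided test as well as pooling.** The only level stated for hypothesis tests is one-sided 5%.
- **Under separate tests no standard error is wrong.** The 9% arises only if either significant result counts as success, and neither document says so. The trial is a pilot with no formal sample size and no success criterion.
- **The SAP may have dropped the IGA and PRO tests.** It says it gives the methods for a complete analysis of Phases I and II, and its Phase II objectives omit both endpoints.

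These points stand and limit the size of the problem. They do not remove it, because the plan leaves open which analysis is meant. Optional second areas also dilute the IGA and PRO results little: the version 1.0 schedule in SAP Appendix 1 lists neither assessment, so the main contributors are the nine subjects who all had two KB103 wounds.

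A further limit concerns IGA itself, which has four ordered levels rather than normal data. In simulations with three subjects and assumed IGA distributions, at least one of two separate tests rejected in only 1.8–5.1% two-sided and 3.2–6.9% one-sided. Pooled error remained raised, at 8–13% two-sided. The normal-theory figure for separate tests should therefore not be carried over to IGA.

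**Conclusion.** The point holds as a gap in specification with a conditional cost. Pooling is invalid wherever a subject has two KB103 wounds. The one-sided inflation to about 8.5–9.5% rests on normal data, equal wound variances and most or all subjects having two; with unequal variances it could be smaller or larger. Among the three version 4.0 subjects alone, the pooled one-sided error lies between 5% and about 9.6%, depending on how many receive a second area. Separate testing is a question of multiplicity, not of a faulty test.

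For wound area the practical effect is confined to the protocol text, because the SAP uses other tests. For IGA and PRO the protocol test is the only one on record, and whether it is still intended needs to be stated. The gap is worth correcting, in proportion to a pilot study.

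**What to change.** In protocol sections 10.5.3 to 10.5.5, state that each subject's KB103 wounds are averaged first, that one KB103-minus-placebo difference is taken per subject, and that one paired test is run on those differences. A mixed model with a subject effect is an acceptable alternative. For IGA, state that codes 5 (cannot be determined) and 6 (not assessed) in section 7.3 are treated as missing and never enter the score as numbers. In the SAP, state whether the IGA and PRO tests are retained and, if so, repeat the rule there.

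The cost is a few sentences, with no new data or visits. Degrees of freedom become the number of subjects minus 1, for example 2 with three subjects. Averaging does not make IGA normal: under one assumed skewed distribution with nine subjects, the averaged one-sided test still rejected in 7.7%. A small-sample t-test on IGA should therefore be described as approximate.
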